Cost-Effectiveness (CE). Complete details of the cost-effectiveness analysis (CEA) will be presented in a separate SAP depending on the outcome of the main study. Briefly, two analyses will be conducted comparing economic outcomes in Intervention – *APOL1* positive and the Control – *APOL1* positive groups. In the first, *within-trial cost analysis*, 6-month total healthcare cost will be estimated per participant using estimates of intervention costs (obtained from Centers for Medicare and Medicaid Services (CMS) physician fee schedule), medication costs (obtained from participant survey, EHR costs per cost center and/or total costs, VAFFS drug prices, National Average Drug Acquisition Cost (NADAC) drug prices, Medicare drug prices), and downstream health care costs of inpatient, outpatient, and emergency department use (from participant survey, EHR costs per cost center and/or total costs, Medicare outpatient prospective payment system (PPS) for healthcare common procedure coding system (HCPCS), cost-to-charge-ratio (CCR) for estimating inpatient costs from charges). The analyses will be adjusted for baseline 3-month total costs and utility scores by means of regression. The second, *long-term CE analysis*, will use a microsimulation model with five health states (Well, Cardiovascular Disease (CVD), ESRD, CVD plus ESRD, and Death) for predicting CE outcomes over a 5-year, 10-year and lifetime horizon following U.S. recommendations. The microsimulation model's predictions of CVD, ESRD and competing mortality rates will be informed by published epidemiological risk models and U.S. life tables. Specifically, we will use the Pooled Cohort Equations for modeling CVD and epidemiological studies for linking CKD stage to long-term ESRD risk with the following risk factors as input parameters: participant demographics (age, gender, and race) obtained from participant surveys; 6-month systolic blood pressure measurements; 6-month smoking status and preventive medication use (BP med) obtained from participant surveys; and 6-month diabetes status, eGFR, urine albumin to creatinine ratio, and blood cholesterol parameters obtained from the EHR. The estimated event rates of CVD, ESRD and competing mortality will be modified using expected rate ratios of blood pressure lowering therapy estimated from difference in 6-month change of systolic blood pressure from baseline. Rate ratios will be based on published meta-analyses of trials on blood pressure lowering medication. The microsimulation model will be used to estimate cumulative costs and QALYs as a function of life expectancy and simulated CVD and ESRD events for each trial participant. Long-term utility and cost penalties

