Data to be used for cost-effectiveness analyses (CEA) will be obtained via participant surveys administered at study visits, direct measurement at study visits (for blood pressure), via the EHR, and via publicly available data sources (CMS physician fee schedule, VAFFS drug prices, NADAC drug prices, Medicare drug prices, PPS for HCPCS, and CCR for estimating inpatient costs from charges). Publicly available data sources can be downloaded freely at the end of the study from corresponding online sources and stored on secure servers at the CC. Any specialized data collection procedures will be presented in the MOP. Details on the data to be used for CEA are presented in Section 9.6.

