- c. Change in documented diagnosis for stage 3 CKD and above is a binary variable (Y/N) where 'Y' is defined as no documented diagnosis at baseline and documented diagnosis at 6 months [No for 3a, Yes for 3b = NY].

4. Documented diagnosis of stage 3 and above CKD by 6 months is a binary variable (Y/N) where 'Y' is defined as (change in documented diagnosis for stage 3 CKD (as described in 3c)) OR (documented diagnosis at baseline (as described in 3a)) [NY, YN or YY].

5. Change in documented diagnosis for any stage CKD from baseline to 6 months (Y/N)

- a. Documented diagnosis at baseline is a binary variable (Y/N) where 'Y' is defined as [the presence of a CKD ICD10 diagnosis code (i.e., N18.x; E08.22; E09.22; E10.22; E11.22; E13.22) in the 24 months prior to baseline].
- b. Documented diagnosis at 6 months is a binary variable (Y/N) where 'Y' is defined as [the presence of a CKD ICD10 diagnosis code (i.e., E18.x; E08.22; E09.22; E10.22; E11.22; E13.22) in the 6 months after baseline].
- c. Change in documented diagnosis for any stage CKD is a binary variable defined as no documented diagnosis at baseline and documented diagnosis at 6 months [No for 5a, Yes for 5b = NY].

6. Documented diagnosis of any stage CKD by 6 months is a binary variable (Y/N) where 'Y' is defined as (the change in documented diagnosis of any stage CKD (as described in 5c)) OR (documented diagnosis at baseline (as described in 5a)) [NY, YN or YY].

For CEA analyses, the following definitions for variables obtained from the EHR will be used:

1. 6-month CKD stage will be defined with the follow categories using the most recent GFR measurement obtained between baseline and 6 months:
  - a. Stage 1 with normal or high GFR (GFR > 90 mL/min)
  - b. Stage 2 Mild CKD (GFR = 60-89 mL/min)
  - c. Stage 3A Moderate CKD (GFR = 45-59 mL/min)
  - d. Stage 3B Moderate CKD (GFR = 30-44 mL/min)
  - e. Stage 4 Severe CKD (GFR = 15-29 mL/min)
  - f. Stage 5 End Stage CKD (GFR <15 mL/min)
2. 6-month blood cholesterol: The last observed blood cholesterol level observed prior to baseline. Missing values will be imputed.

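### As summarised in Section 9.6, the exploratory long-term cost-effectiveness model lets the SBP effect on CVD enter twice: through 6-month SBP in the risk model and again through a rate ratio for SBP change

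*Combined protocol and SAP*

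**What the plan says.** The long-term analysis in Section 9.6 (Cost-Effectiveness) is a microsimulation comparing the two *APOL1*-positive groups. It is described in two consecutive steps.

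1. **Predict event rates.** The Pooled Cohort Equations are named for CVD, and epidemiological studies linking CKD stage to ESRD are named for ESRD. One shared list of inputs follows, which includes "6-month systolic blood pressure measurements; 6-month smoking status and preventive medication use (BP med) obtained from participant surveys".
2. **Modify those rates.** For CVD, for ESRD and for deaths from competing causes alike, the rates so obtained "will be modified using expected rate ratios of blood pressure lowering therapy estimated from difference in 6-month change of systolic blood pressure from baseline". The rate ratios are to come from published meta-analyses of blood-pressure-lowering trials; no value is given.

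The model is then used "to estimate cumulative costs and QALYs as a function of life expectancy and simulated CVD and ESRD events for each trial participant".

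Three other statements bear on the reading:

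- Section 9.6 says that complete details "will be presented in a separate SAP depending on the outcome of the main study", and marks its own account as brief.
- Section 10.1 points back to the same place: "Details on the data to be used for CEA are presented in Section 9.6".
- Section 10.2 gives one cost-effectiveness input a definition that departs from its label: "6-month blood cholesterol: The last observed blood cholesterol level observed prior to baseline". It gives no such definition for SBP.

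The Synopsis and Section 2.2 class cost-effectiveness as exploratory.

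**The concern.** A participant's 6-month SBP is baseline SBP plus the change since baseline. If the intervention lowers SBP, intervention participants enter the CVD risk model with lower SBP, and their predicted CVD rate is already lower. Multiplying that rate by a ratio derived from the same SBP change credits the reduction again. BP-medication use at 6 months is also post-randomisation, so it too can carry a difference between groups into the first step.

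CVD events drive part of the modelled QALYs and costs. Those outputs would then rest on an SBP effect different from the one measured in the trial. The full specification may also be written after the SBP result is known, so it is better to settle the matter in advance.

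**Working it through.** **Figures in the plan.** The documents state no cost-effectiveness result, rate ratio or SBP coefficient, so there is nothing of that kind to reproduce. The only design figure borrowed here is the 3.5 mm Hg difference in Section 9.1. It does reproduce: 844/2 = 422 per group, SD 18.1 and two-sided alpha 0.0492 give power 0.800. That supports 3.5 mm Hg as the design value and has no bearing on the structural point.

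**Structure.** Let D be the size of the between-group SBP reduction at 6 months, with no baseline difference. Let s be the CVD rate ratio per 10 mm Hg implied by the risk model, and r the ratio per 10 mm Hg from the meta-analyses.

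- Step 1 contributes s^(D/10).
- Step 2 multiplies by r^(D/10).
- As written, the CVD rate ratio is s^(D/10) × r^(D/10). Counted once, it is r^(D/10).
- With s = r, the log effect doubles.

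**Does other text block step 1?**

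- Nothing restricts the SBP input to baseline, to the control group or to a common cohort.
- The regression adjustment in Section 9.6 ("The analyses will be adjusted for baseline 3-month total costs and utility scores by means of regression") belongs to the within-trial cost analysis and comes before the long-term model is introduced.
- If the difference in change means each participant's own change from baseline, the overlap remains, because 6-month SBP includes that change.

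**Illustration.** Assumptions: D = 3.5 mm Hg (a 3-month design value assumed to hold at 6 months), no baseline difference, s = r.

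| Ratio per 10 mm Hg (assumed) | Counted once: 1 − r^0.35 | Counted twice: 1 − r^0.70 |
|---|---|---|
| 0.75 | 1 − 0.904 = 9.6% | 1 − 0.818 = 18.2% |
| 0.80 | 1 − 0.925 = 7.5% | 1 − 0.855 = 14.5% |
| 0.90 | 1 − 0.964 = 3.6% | 1 − 0.929 = 7.1% |

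**Unequal slopes.** With r = 0.80 and s = 0.90, the combined ratio is 0.9249 × 0.9638 = 0.8914, a 10.9% reduction against 7.5%. If both vary separately over 0.70 to 0.90, the reduction is 1.27 to 4.12 times that from the rate ratio alone. The existence of the overlap does not depend on these values; its size does.

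**The case against.** **The text is a summary.** This is the strongest objection. Section 9.6 leaves the details to another SAP, which could name a reference strategy or a starting SBP and so remove the overlap. That limits certainty about what will be done. It does not change what the two stated steps do when followed, and Section 10.1 sends the reader to 9.6 for the data details.

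**The 6-month label may be loose.** Section 10.2 shows that one 6-month input is really a pre-baseline value. Section 10.1 says that blood pressure is measured directly at study visits, but that includes the baseline visit and settles nothing. The reading therefore rests on the SBP phrase in 9.6. This objection stands as a reason to clarify.

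**The input list is shared.** It does not allocate SBP between the CVD and ESRD models. The plain reading puts SBP in the CVD model. A reader might infer the same overlap for ESRD and mortality, but the text does not support that: ESRD is described through CKD stage, and competing mortality draws on published risk models and life tables without a stated SBP route.

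**Baseline imbalance.** Section 9.6 warns that the *APOL1*-positive groups may differ at baseline. A reader might infer that a baseline SBP difference could turn the overstatement into an understatement. Let B be the baseline difference and C the difference in change. With equal slopes the as-written SBP term is (B + C) + C = B + 2C. Comparing this with C alone uses the wrong benchmark when B is not zero. With equal variances and baseline-to-6-month correlation ρ, the baseline-adjusted effect is (B + C) − ρB = C + (1 − ρ)B. Section 9.1 uses 18.1 both as the SBP SD and in the calculation for change. Taken together with equal variances, that gives 2(1 − ρ) = 1, so ρ = 0.5, and B + 2C = 2(C + 0.5B): twice the adjusted effect for every B. Another ρ would shift the multiple, but the use of an unadjusted 6-month level is a separate matter from counting the effect twice.

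**Conclusion.** The concern holds for CVD in the exploratory long-term model as Section 9.6 summarises it: the stated steps apply the SBP effect twice. With equal slopes and no baseline difference the log effect doubles; at an assumed 0.80 per 10 mm Hg and 3.5 mm Hg, a 7.5% reduction becomes 14.5%. The slopes and the carry-over from 3 to 6 months are assumptions.

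A reader might also infer that the cost-effectiveness ratio will be biased in favour of the intervention by a known amount, or that the plan intends to choose the method after seeing the SBP result. Neither is supported. The documents give no costs, utilities or coefficients from which to derive the ratio, and the wording on the separate SAP allows late specification without stating that purpose.

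Priority is low. The primary endpoint, alpha and sample size are unaffected.

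**What to change.** In Section 9.6 and in the cost-effectiveness SAP, before the SBP result is known, state that the SBP effect on CVD is applied once, by one of two routes:

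- **(a)** Predict CVD from baseline SBP and BP-medication values that do not differ by strategy, and apply the rate ratio for the baseline-adjusted 6-month SBP difference to the intervention strategy only.
- **(b)** Use 6-month SBP in the risk model, adjusted for baseline SBP, and apply no SBP-derived rate ratio to CVD.

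Under either route, name the SBP time point, the reference strategy and the event rates that the ratio multiplies.

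The cost is a few sentences and changed model inputs. No new visits or SBP data are needed, since SBP is measured at baseline (Section 7.2) and at follow-up visits (Section 7.3). For (a), confirm the source of baseline BP-medication status, which the survey description in Section 7.2 does not name. If it is incomplete, one common value for both strategies will serve.

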#### Long-Term Exploratory Outcomes:

Research participants can consent for long-term follow up of kidney function. We will use appropriate procedures (including secure linkage, honest broker procedures, etc.) to access several databases, including patient electronic medical records, or restricted databases such as USRDS (United States Renal Data System) and CMS to track kidney function measurements, blood pressure, medication usage and health outcomes related to kidney disease up to 10 years from the date of enrollment, for patients who agree. We will then analyze these data as part of our exploratory outcomes and assess effect of interventions on long-term kidney outcomes.

#### Impact of Social Determinants of Health:

Data from participant surveys will be used to explore the impact of individual-level social determinants of health on primary, secondary, and exploratory study outcomes. Participant address will be used for linkage to publicly available data on community-level determinants of health (eg, Social CDC Vulnerability Index).

### **9.7      Interim Analyses**

A single planned interim analysis was planned initially for this study. To account for repeated significance testing of the accumulating data, the group sequential method of Lan and DeMets will be used as a guide for interpreting this interim analysis. Monitoring boundaries for the primary endpoint will be based on a two-sided symmetric Lan-DeMets spending function using O'Brien-Fleming type boundaries with an overall two-sided significance level of  $\alpha=0.05$ . The O'Brien-Fleming approach requires large critical values early in the study but relaxes (i.e., decreases) the critical value as the trial progresses. The primary and interim analyses will compare SBP at 3 months among *APOL1* positive individuals in the Control arm to *APOL1* positive individuals in the Intervention arm. Because *APOL1* genotype (i.e., positive vs. negative) for participants in the Control arm is determined around the time of the 6 month study visit, only participants that have completed their 6 month study visit will be included in the interim analysis. To account for the delays in receiving genetic testing results, the interim analysis will be targeted to occur when approximately 25% of the participants have completed their 6 month study visit. Using the O'Brien-Fleming type boundary at 25% information, if the analysis calculates a p-value that is less than 0.00009, stopping the trial for efficacy or harm will be proposed. In order to maintain the overall significance level of 0.05, the final analysis of the primary endpoint will be considered significant for p-values less than 0.049975.

If the interim analysis does not propose stopping for efficacy (p-value <0.00009 and the intervention has the larger reduction in SBP at 3 months), then the conditional power to detect a significant result at the end of the trial will be estimated. The conditional power will be presented to the DSMB to facilitate discussion of whether the trial should be stopped for futility.

An additional interim analysis was performed per request by the DSMB in May, 2022. In order to maintain the overall significance level of 0.05 after this second interim analysis, the definition of significant p-value for the final analysis is recalculated by continuing to use the Lan-DeMets function with O'Brien-Fleming type boundaries appropriately for the approximate percent information at which the interim analysis occurred. Due to the occurrence of this second interim analysis, the final analysis of the primary endpoint will be considered significant if p-value is less than 0.0492.

## **9.8 Handling of Missing Data**

For the primary and secondary statistical analyses described above, multiple imputation will be used for all missing values except those due to participant death. To ensure that the missing at random assumption for multiple imputation is valid, we will compare baseline SBP and other patient characteristics in those lost to follow up to participants retained on their randomization assignment. We will also do sensitivity analyses where we compare results obtained with multiple imputation to those obtained without imputation. Missing values due to death will not be imputed and will therefore not be included in the analyses.

For exploratory repeated measures analyses, missing data are easily handled in repeated measures mixed models, as long as the missing at random assumption is valid. However, the missing at random assumption cannot be tested. Accordingly, for exploratory analyses using repeated measures mixed models, we will also conduct a sensitivity analysis where missing values are imputed using multiple imputation. The results with and without multiple imputation will be compared. More complete details of the handling of missing values under different circumstances will be described in the SAP.

## **9.9 Multiplicity**

With the primary and various secondary endpoints that have been outlined, there is a multiplicity of analyses to be performed, which leads to an increased probability that at least one of the comparisons could be "significant" by chance. Adjusting for the effects of the repeated significance testing for the multiplicity of secondary endpoints would require that very small significance levels be used for every comparison. Therefore, rather than adjusting for multiple comparisons, statistical results (e.g., p values) will only be presented for the primary endpoint analysis. We will be conservative in the interpretation of secondary analyses and report only point estimates and 95% confidence intervals. We have also pre-specified the primary and secondary outcome variables to avoid over-interpretation of strictly exploratory comparisons.

## 10. DATA MANAGEMENT

### 10.1 Data Entry and Record Keeping

GUARDD-US will have 4 main data sources: data collected from participants (survey, blood pressure and pulse) and providers (survey), genetic testing results from designated laboratories, data from the EHR, and publicly available data for CEA analyses. Data from patients and providers should be entered directly into study database by trained and qualified personnel at each clinical site. Site staff will receive training on the use of the study database. After staff are trained, they will receive a unique user identification and password to access data entry forms for their site. Access codes should not be shared and are non-transferable.

Laboratories will transfer genetic testing results to the IGNITE PTN CC and follow standard site-specific return of results procedures for providers. The genotype and result (i.e., positive versus negative) for each participant will then be automatically imported to the participant's study database record from laboratory produced output files. The accuracy of the automatic import of laboratory results will be verified by comparing the results recorded in the study database to an external record of the result for a subset of the study participants.

Sites will extract the relevant data from their EHR (see Section 7.7) and transfer those data to the IGNITE PTN CC following procedures that will be specified. Briefly, sites will be given a list of information to extract for their GUARDD-US participants, a common format that data should be converted to, and procedures for secure file transfer to the CC. Transfers of data will occur after at least 25% of the participants have completed their 6 month visit and 6-12 months after the last participant is randomized.

Data to be used for cost-effectiveness analyses (CEA) will be obtained via participant surveys administered at study visits, direct measurement at study visits (for blood pressure), via the EHR, and via publicly available data sources (CMS physician fee schedule, VAFFS drug prices, NADAC drug prices, Medicare drug prices, PPS for HCPCS, and CCR for estimating inpatient costs from charges). Publicly available data sources can be downloaded freely at the end of the study from corresponding online sources and stored on secure servers at the CC. Any specialized data collection procedures will be presented in the MOP. Details on the data to be used for CEA are presented in Section 9.6.

### 10.2 Data Element Definitions

Baseline SBP will be defined as the mean of the 2nd and 3rd measurements taken according to the GUARDD-US Blood Pressure Protocol provided in the MOP. Similarly, follow-up SBP will be the average of the 2nd and 3rd SBP measures at the follow-up visit, or alternatively the SBP from the EHR entered into the study database by the site in accordance with the study manual of procedures (MOP).

Secondary Endpoints will be defined as follows:

1. Change in urine microalbuminuria/proteinuria orders from baseline to 6 months (Y/N)
  - a. Order of urine microalbuminuria/proteinuria test at baseline is a binary variable (Y/N) where 'Y' is defined as the presence of urine proteinuria or urine microalbuminuria diagnostic code (i.e. 82043/84156 (Current Procedural Terminology (CPT) codes) OR the presence of urine microalbuminuria/proteinuria lab test order and/or result in the participant's EHR record at any point in the 12 months prior to baseline.
  - b. Order of urine microalbuminuria/proteinuria test at 6 months is a binary variable (Y/N) where 'Y' is defined as the presence of urine proteinuria or urine microalbuminuria diagnostic code 82043/84156 (CPT codes) OR the presence of urine microalbuminuria/proteinuria lab test order and/or result in the participant's EHR record at any point from baseline to 6 months.

- c. Change in urine microalbuminuria/proteinuria orders is a binary variable (Y/N) where 'Y' is defined as no order of urine microalbuminuria/proteinuria test at baseline and having an order of urine microalbuminuria/proteinuria test at 6 months [No for 1a, Yes for 1b = NY].

2. Documented order of microalbuminuria/proteinuria tests by 6 months is a binary variable (Y/N) where 'Y' is defined as the change in urine microalbuminuria/proteinuria orders (as described in 1c) OR (order of urine microalbuminuria/proteinuria test at baseline) [NY, YN or YY]

3. Change in documented diagnosis for stage 3 CKD and above from baseline to 6 months (Y/N)

- a. Documented diagnosis at baseline is a binary variable (Y/N) where 'Y' is defined as [the presence of a CKD ICD10 diagnosis codes of N18.3 – N18.5 in the 24 months prior to baseline].
- b. Documented diagnosis at 6 months is a binary variable (Y/N) where 'Y' is defined as [the presence of a CKD ICD10 diagnosis codes of N18.3 – N18.6 in the 6 months after baseline].
- c. Change in documented diagnosis for stage 3 CKD and above is a binary variable (Y/N) where 'Y' is defined as no documented diagnosis at baseline and documented diagnosis at 6 months [No for 3a, Yes for 3b = NY].

4. Documented diagnosis of stage 3 and above CKD by 6 months is a binary variable (Y/N) where 'Y' is defined as (change in documented diagnosis for stage 3 CKD (as described in 3c)) OR (documented diagnosis at baseline (as described in 3a)) [NY, YN or YY].

5. Change in documented diagnosis for any stage CKD from baseline to 6 months (Y/N)

- a. Documented diagnosis at baseline is a binary variable (Y/N) where 'Y' is defined as [the presence of a CKD ICD10 diagnosis code (i.e., N18.x; E08.22; E09.22; E10.22; E11.22; E13.22) in the 24 months prior to baseline].
- b. Documented diagnosis at 6 months is a binary variable (Y/N) where 'Y' is defined as [the presence of a CKD ICD10 diagnosis code (i.e., E18.x; E08.22; E09.22; E10.22; E11.22; E13.22) in the 6 months after baseline].
- c. Change in documented diagnosis for any stage CKD is a binary variable defined as no documented diagnosis at baseline and documented diagnosis at 6 months [No for 5a, Yes for 5b = NY].

6. Documented diagnosis of any stage CKD by 6 months is a binary variable (Y/N) where 'Y' is defined as (the change in documented diagnosis of any stage CKD (as described in 5c)) OR (documented diagnosis at baseline (as described in 5a)) [NY, YN or YY].

For CEA analyses, the following definitions for variables obtained from the EHR will be used:

1. 6-month CKD stage will be defined with the follow categories using the most recent GFR measurement obtained between baseline and 6 months:
  - a. Stage 1 with normal or high GFR (GFR > 90 mL/min)
  - b. Stage 2 Mild CKD (GFR = 60-89 mL/min)
  - c. Stage 3A Moderate CKD (GFR = 45-59 mL/min)
  - d. Stage 3B Moderate CKD (GFR = 30-44 mL/min)
  - e. Stage 4 Severe CKD (GFR = 15-29 mL/min)
  - f. Stage 5 End Stage CKD (GFR <15 mL/min)
2. 6-month blood cholesterol: The last observed blood cholesterol level observed prior to baseline. Missing values will be imputed.

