## 9. STATISTICAL ANALYSIS PLAN AND SAMPLE SIZE

### 9.1 Sample Size Determination

#### Main Study

In GUARDD, there was a 13% prevalence of *APOL1* positive individuals among hypertension participants and a standard deviation of 18.1 mm Hg for SBP. A separate unpublished pilot study from Indiana University showed a 20% prevalence of *APOL1* positive individuals among participants with CKD and an estimated CKD prevalence of 50%. Finally, another study showed a 26% prevalence of *APOL1* positive AAs with CKD. As such, the initial sample size determination assumed a 17% prevalence of *APOL1* positive individuals. However, observation of the prevalence of the *APOL1* positive study participants during the course of the study led investigators and the DSMB to believe that this assumption was too high and the actual prevalence in the study population was between 14 and 15 percent. Assuming a conservative 14% prevalence of *APOL1* positive individuals based on these studies, a sample size of approximately 6700 for the randomized population would result in approximately 938 *APOL1* positive individuals with at least 469 in each arm for the main study population examined here. Using a two tailed t-test and assuming an overall 5% level of significance, 10% lost-to-follow up, two interim analyses, and a standard deviation of 18.1 mm of Hg, a sample size of 6700 for the randomized population and approximately 938 for the *APOL1* positive individuals will detect a 3.5 mm Hg difference in the change in SBP from baseline to 3 months between Intervention - *APOL1* positive and Control - *APOL1* positive groups with at least 80% power. This sample size determination assumes 10% of the 938 *APOL1* positive individuals could drop out of the study before 3 months and therefore have incomplete data on SBP change from baseline to 3 months. *APOL1* positive individuals with incomplete data on SBP change from baseline to 3 months cannot be included in the primary endpoint analysis. Therefore, the final analysis on the primary endpoint needs at least 844 *APOL1* positive individuals who have complete data for SBP change from baseline to 3 months to detect a 3.5 mm Hg difference between two treatment groups. Enrollment will continue until the 844 target can be ensured. Since *APOL1* and SBP data could be missing for various reasons, approximately 50 additional participants will be randomized to help us to reach this 844 target. This makes the total randomization target to be approximately 6750. Enrollment may end prior to the 6750 target if the study team is certain that the necessary 844 *APOL1* positive individuals with complete SBP change data can be achieved.

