## **9.3 Population for Analyses**

### Population for Main Study Objectives

Participants from the Randomized Population who test positive for *APOL1*.

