## **9.5 Analysis of the Secondary Endpoints**

The effect of knowledge of a positive *APOL1* status on secondary endpoints [i.e., change in urine microalbuminuria/proteinuria orders from baseline to 6 months (Y/N), documented order of microalbuminuria/proteinuria tests by 6 months (Y/N), change in documented diagnosis for stage 3 CKD and above (Y/N) from baseline to 6 months, documented diagnosis of CKD stage 3 and above by 6 months (Y/N), change in documented diagnosis for any stage CKD from baseline to 6 months (Y/N), and documented diagnosis of all stages of CKD by 6 months (Y/N) ] will be compared between Intervention - *APOL1* positives and Control - *APOL1* positives with the proportion difference test.

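### Secondary endpoint 1 can be met only by participants with no urine-test order in the prior year, yet it is compared over all APOL1 positives, so its risk difference is scaled down by the share at risk

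*Combined protocol and SAP*

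**What the plan says.** Section 10.2 builds endpoint 1 from two indicators. Item 1a is Yes if a urine microalbumin or protein test appears in the "EHR record at any point in the 12 months prior to baseline". Item 1b is Yes if one appears from baseline to 6 months. Item 1c scores the endpoint Y for "no order of urine microalbuminuria/proteinuria test at baseline and having an order of urine microalbuminuria/proteinuria test at 6 months", the pattern labelled NY. The other three patterns (NN, YN, YY) score N.

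The main-study population in section 9.3 is "Participants from the Randomized Population who test positive for" APOL1. Section 9.5 compares all six secondary endpoints between the Intervention and Control APOL1 positives "with the proportion difference test", with no restriction to, or stratification by, item 1a. Under section 9.9 the secondary analyses will "report only point estimates and 95% confidence intervals", without p-values.

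Endpoint 2 is Y for NY, YN or YY. Endpoints 3 and 5 (new CKD diagnosis codes) have the same NY structure as endpoint 1, with a 24-month look-back.

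**The concern.** The denominator includes people in whom the event cannot occur. A participant tested both before and after baseline gets the same score as one never tested. The between-arm difference therefore depends on the effect of returning results and also on how many participants happened to have a prior order.

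That share is above zero by design. CKD criterion B in section 5.1 admits people on albuminuria or proteinuria values, looked for first within 12 months of enrolment. Those who qualify on a value inside the 1a window will nearly all be Yes for 1a.

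Because section 9.9 reports only estimates and intervals, the size of the difference is what readers will take away. They cannot convert it to the effect among people who could be newly tested unless the 1a share is reported, and the plan does not call for that. Section 9.6 notes that the APOL1-positive groups may differ at baseline, but provides covariate adjustment only in the SBP mixed models, not for the secondary endpoints.

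**Working it through.** **The plan's own figures.** The documents give no rate, power or sample size for endpoint 1. The number per arm comes from section 9.1: 6700 × 0.14 = 938 APOL1 positives, "with at least 469 in each arm for the main study population examined here". The SBP calculation behind it reproduces: SD 18.1, difference 3.5, 80% power and final two-sided alpha 0.0492 (section 9.7) give 422 per arm, or 844, and 844 / 0.90 = 938. This fixes N = 469 per arm and has no other bearing here.

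**Assumed inputs.**
- q, the share with 1a = Yes: not given; 0.2 to 0.7 tried. The only related figure (section 2.1) is that urine protein tests are missing in up to 30% of people with CKD.
- Order rates among those with no prior order: not given. The pilot's 20% v 29% (section 2.1) serve as stand-ins. They are 12-month renal-testing rates in a population without CKD or diabetes, not 6-month urine orders.

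**Formulas**, with p0 and p1 the at-risk rates:
- All positives: RD = (1 − q)(p1 − p0).
- Variance in one arm: (1 − q)p[1 − (1 − q)p]/N = [(1 − q)p(1 − p) + q(1 − q)p²]/N. The second term is the noise from chance variation in 1a; standardising over 1a removes it.
- At risk only: RD = p1 − p0, with N(1 − q) per arm.
- The half-width is 1.96 × SE. The standardised half-width is (1 − q) × the at-risk half-width; the contribution from estimating q is negligible.

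**Worked case, q = 0.5.** RD over all positives = 0.5 × 9.0 = 4.5 points. The first variance terms sum to 0.5 × 0.16 + 0.5 × 0.2059 = 0.18295. The second sum to 0.25 × 0.04 + 0.25 × 0.0841 = 0.03103. Unadjusted half-width = 1.96 × √(0.21398/469) = 4.2 points. Standardised half-width = 1.96 × √(0.18295/469) = 3.9 points. A simulation of 200,000 trials gave 4.5 ± 4.2 for all positives and 9.0 ± 7.8 at risk.

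**Results (percentage points, 20% v 29% at risk).**

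| q | All positives: RD ± half-width | At risk: n per arm, RD ± half-width | Half-width / RD, all v at risk | Power, all v at risk | All positives, standardised half-width |
|---|---|---|---|---|---|
| 0.2 | 7.2 ± 5.1 | 375, 9.0 ± 6.1 | 0.70 v 0.68 | 79% v 82% | 4.9 |
| 0.3 | 6.3 ± 4.8 | 328, 9.0 ± 6.5 | 0.76 v 0.73 | 73% v 77% | 4.6 |
| 0.5 | 4.5 ± 4.2 | 234, 9.0 ± 7.7 | 0.93 v 0.86 | 56% v 62% | 3.9 |
| 0.7 | 2.7 ± 3.3 | 140, 9.0 ± 10.0 | 1.23 v 1.11 | 35% v 42% | 3.0 |

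Standardising narrows the all-positive interval by about 3%, 5%, 8% and 10% down the rows, with the estimated quantity unchanged.

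**Other rates.** The ratio of z statistics, all to at risk, is about √[(1 − p)/(1 − (1 − q)p)], below 1 whenever q > 0. Over at-risk rates of 10 v 15%, 20 v 29%, 30 v 40% and 50 v 60%, and q from 0.2 to 0.7, the loss in z runs from 1.5% (10 v 15%, q = 0.2) to 27% (50 v 60%, q = 0.7).

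**Endpoint 2 does not remove the dilution.** It scores everyone with a prior order Y, so its expected RD is also (1 − q)(p1 − p0), with a half-width of 6.2 points at q = 0.5.

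**The case against.** The strongest reply is that this is a choice of estimand. The aims concern the probability of receiving a urine test among APOL1 positives, without restriction to those not recently tested, and new orders per APOL1-positive participant is a legitimate quantity, estimated without bias by a fully randomised comparison. This stands.

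A reader might make three stronger inferences, none of which the documents support:
- That the planned estimate is biased, or driven by prior orders as much as by the intervention. If returning results has no effect, the expected difference is zero at any q. Chance imbalance in 1a is already reflected in the standard error.
- That the planned interval is wider. It is narrower in absolute terms (4.2 v 7.7 points at q = 0.5). The loss is only relative to the effect, and is modest with the stand-in rates.
- That the at-risk group should replace the planned population. It answers a narrower question. It also says nothing about repeat testing in people already tested, which only a comparison of 1b over all positives would show.

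Two further points stand. The plan sets no power target for secondary endpoints, so power is only a yardstick here. The separate SAP mentioned in section 9.2 is not among the documents and may already contain such an analysis.

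None of this answers the remaining gap: nothing in sections 9.3, 9.5 or 10.2 conditions on 1a or lets a reader recover the at-risk effect.

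**Conclusion.** The structural point holds on the text alone: participants with a prior order cannot meet endpoint 1 but stay in its denominator, so the planned risk difference is the at-risk difference times the share with no prior order. The consequence is one of interpretation and some avoidable noise, not of validity.

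The size depends on q and the at-risk order rates, both assumed. For q between 0.2 and 0.7 the reported difference is 20% to 70% smaller than the difference among those at risk. With 20% v 29%, power is about 2 to 7 points lower than in the at-risk comparison. Higher at-risk rates would make the loss larger, and lower rates smaller.

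**What to change.** In section 9.5, prespecify two estimates for endpoint 1, reported together:
1. The difference by randomised arm in the proportion with an order after randomisation (1b = Yes), among APOL1 positives with 1a = No. Item 1a is fixed before randomisation, so the comparison remains randomised.
2. The planned NY difference over all APOL1 positives, stratified by or standardised over 1a.

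Report the 1a share by arm. Do the same for endpoints 3 and 5, using 3a = No and 5a = No.

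The cost is SAP wording, since 1a and 1b are already derived. Because section 9.8 multiply imputes missing values for secondary analyses, the text should say how at-risk membership is set when 1a is missing. As the trial is unblinded, the change should be dated before secondary-endpoint results by arm are examined. The downside is that the at-risk estimate uses fewer people, has a wider absolute interval, and applies only to those without a prior order or diagnosis. The all-positive figure beside it covers the rest.
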